8.2 Safety assessments

Planned time points for all safety assessments are provided in the SoA.

8.2.1 Clinical safety laboratory assessments

Blood and urine samples for determination of clinical chemistry, hematology, and urinalysis will be taken at the times indicated in the assessment schedules and as clinically indicated (see the SoAs).

Clinical laboratory safety tests, including serum pregnancy tests, will be performed in a licensed clinical laboratory according to local standard procedures. Sample tubes and sample sizes may vary depending on the laboratory method used and routine practice at the site. Pregnancy tests

may be performed at the site using a licensed test (urine or serum pregnancy test). Abnormal clinically significant laboratory results should be repeated as soon as possible (preferably within 24 to 48 hours).

Additional safety samples may be collected if clinically indicated at the discretion of the Investigator. The date, time of collection, and results (values, units, and reference ranges) will be recorded on the appropriate eCRF.

The laboratory variables to be measured are presented in Table 8 (clinical chemistry), Table 9 (hematology), and Table 10 (urinalysis).

Other safety tests to be performed at screening include assessment for hepatitis B surface antigen, hepatitis C antibodies, and HIV antibodies.

The following laboratory variables will be measured:

Table 8 Clinical chemistry

Albumin	Lipase ^b
Alkaline phosphatase	Magnesium ^c
ALT ^a	Potassium
Amylase ^b	Sodium
AST ^a	Total bilirubin ^a
Bicarbonate ^c	Total protein
Calcium	TSH ^e
Chloride ^c	T3 free ^f (reflex)
Creatinine ^d	T4 free ^f (reflex)
Gamma glutamyltransferase ^c	Urea or blood urea nitrogen, depending on local practice
Glucose	
Lactate dehydrogenase	

^a Tests for ALT, AST, alkaline phosphatase, and total bilirubin must be conducted and assessed concurrently. If total bilirubin is $\geq 2 \times$ upper limit of normal (and no evidence of Gilbert's syndrome), then fractionate into direct and indirect bilirubin.

^b It is preferable that both amylase and lipase parameters are assessed. For sites where only 1 of these parameters is routinely measured, either lipase or amylase is acceptable.

^c Bicarbonate (where available), chloride, creatinine clearance, gamma glutamyltransferase, magnesium, testing are to be performed at baseline, on Day 1 (unless all screening laboratory clinical chemistry assessments are performed within 3 days prior to Day 1), and if clinically indicated.

^d Creatinine clearance will be calculated by data management using Cockcroft-Gault (using actual body weight).

^e If TSH is measured within 14 days prior to Day 1 (first infusion day), it does not need to be repeated at Day 1.

^f Free T3 or free T4 will only be measured if TSH is abnormal or if there is a clinical suspicion of an AE related to the endocrine system.

ALT Alanine aminotransferase; AST Aspartate aminotransferase, TSH Thyroid-stimulating hormone.

Table 9 Hematology

Absolute neutrophil count ^a	Absolute lymphocyte count ^a
Hemoglobin	Platelet count
Total white cell count	

Note: For coagulation parameters, activated partial thromboplastin time [either as a ratio or as an absolute value, in seconds] and international normalized ratio are to be assessed at baseline on Day 1 (unless all screening laboratory hematology assessments are performed within 3 days prior to Day 1), and as clinically indicated.

^a Can be recorded as absolute counts or as percentages. Absolute counts will be calculated by Data Management if entered as percentage. Total white cell count therefore has to be provided.

Table 10 Urinalysis

Bilirubin	Ketones
Blood	pH
Color and appearance	Protein
Glucose	Specific gravity

Note: Urinalysis should be done at baseline (screening) and then as clinically indicated.

Note: Microscopy is preferred to investigate white blood cells, with use of high power field for red and white blood cells; dipstick can be used as well.

If a patient shows an AST or ALT $\geq 3 \times$ ULN together with total bilirubin $\geq 2 \times$ ULN, refer to 0 for further instructions on cases of increases in liver biochemistry and evaluation of Hy's Law. These cases should be reported as SAEs if, after evaluation, they meet the criteria for a Hy's law case or if any of the individual liver test parameters fulfill any of the SAE criteria.

All patients should have further chemistry profiles performed at 30 days (± 3 days), 2 months (± 1 week), and 3 months (± 1 week) after permanent discontinuation of IP (see the SoAs).

Any clinically significant abnormal laboratory values should be repeated as clinically indicated and recorded on the eCRF. Situations in which laboratory safety results should be reported as AEs are described in Section 8.3.7.

All patients with Grade 3 or 4 laboratory values at the time of completion or discontinuation from IP must have further tests performed until the laboratory values have returned to Grade 1 or 2, unless these values are not likely to improve because of the underlying disease.

8.2.2 Physical examinations

Physical examinations will be performed according to the assessment schedules (see the SoAs). Full physical examinations will include assessments of the head, eyes, ears, nose, and throat and the respiratory, cardiovascular, GI, urogenital, musculoskeletal, neurological, dermatological, hematologic/lymphatic, and endocrine systems. Height will be measured at screening only. Targeted physical examinations are to be utilized by the Investigator on the basis of clinical observations and symptomatology. Situations in which physical examination results should be reported as AEs are described in Section 8.3.7.

8.2.3 Vital signs

Vital signs (blood pressure [BP], pulse, temperature, and respiration rate) will be evaluated according to the SoAs. Body weight is also recorded at each visit along with vital signs.

First infusion

On the first durvalumab infusion, patients will be monitored and vital signs collected/recorded in eCRF prior to, during, and after infusion of IP as presented in the bulleted list below.

BP and pulse will be collected from patients before, during, and after each infusion at the following times (based on a 60-minute infusion):

- Prior to the beginning of the infusion (measured once from approximately 30 minutes before up to 0 minutes [ie, the beginning of the infusion])
- Approximately 30 minutes during the infusion (**halfway** through infusion)
- At the end of the infusion (approximately 60 minutes \pm 5 minutes)

If the infusion takes longer than 60 minutes, then BP and pulse measurements should follow the principles as described above or be taken more frequently if clinically indicated. A 1-hour observation period is recommended after the first infusion of durvalumab and EP.

Subsequent infusions

BP, pulse, and other vital signs should be measured, collected/recorded in eCRF prior to the start of the infusion. Patients should be carefully monitored and BP and other vital signs should be measured during and post infusion as per institution standard and as clinically indicated. Any clinically significant changes in vital signs should be entered onto an unscheduled vital signs CRF page.

Situations in which vital signs results should be reported as AEs are described in Section 8.3.7. For any AEs of infusion reactions, the vital signs values should be entered into the CRF.

8.2.4 Electrocardiograms

Resting 12-lead ECGs will be recorded at screening and as clinically indicated throughout the study (see the SoAs). ECGs should be obtained after the patient has been in a supine position for 5 minutes and recorded while the patient remains in that position.

In case of clinically significant ECG abnormalities, including a QTcF value >470 ms, 2 additional 12-lead ECGs should be obtained over a brief period (eg, 30 minutes) to confirm the finding.

Situations in which ECG results should be reported as AEs are described in Section 8.3.7.

8.2.5 Early patient review for safety

Not applicable.

8.2.6 WHO/ECOG performance status

WHO/ECOG performance status will be assessed at the times specified in the assessment schedules (see the SoAs) based on the following:

0. Fully active; able to carry out all usual activities without restrictions
1. Restricted in strenuous activity, but ambulatory and able to carry out light work or work of a sedentary nature (eg, light housework or office work)
2. Ambulatory and capable of self-care, but unable to carry out any work activities; up and about more than 50% of waking hours.
3. Capable of only limited self-care; confined to bed or chair more than 50% of waking hours
4. Completely disabled; unable to carry out any self-care and totally confined to bed or chair
5. Dead

Any significant change from baseline or screening must be reported as an AE.

8.2.7 Patient reported outcomes (PRO)

–PRO” is an umbrella term referring to all outcomes and symptoms that are directly reported by the patient. PROs have become a significant endpoint when evaluating effectiveness of treatments in clinical studies. The following PROs will be administered in this study: EORTC QLQ-C30 v3 (core questionnaire), EORTC QLQ-LC13 (lung cancer module), patient-reported outcomes version of the CTCAE (PRO-CTCAE). (see [Appendix H and I](#)).

The PRO instruments will be completed by the patients using a paper format questionnaire on day 1 of every cycle. All assessments should be completed without assistance from anyone according to the assessment schedules. It takes approximately 30 minutes for patients to complete the questionnaires; therefore, the burden to the patient is moderate.

8.2.7.1 EORTC QLQ-C30

The EORTC QLQ-C30 v3 questionnaire is included for the purpose of assessing HRQoL and is a well-established measure of HRQoL/health status and commonly used as an endpoint in cancer clinical studies. It assesses HRQoL/health status through 9 multi-item scales: 5 functional scales (physical, role, cognitive, emotional, and social), 3 symptom scales (fatigue, pain, and nausea and vomiting), and a global health and quality-of-life (QoL) scale. Six single-item symptom measures are also included dyspnea, insomnia, appetite loss, constipation, diarrhea, and financial difficulties (see Appendix H). For each of the 15 domains, final scores are transformed such that they range from 0 to 100, where higher scores indicate greater functioning, greater HRQoL, or

greater level of symptoms (Aaronson et al 1993).

8.2.7.2 EORTC QLQ-LC13

For patients with SCLC, a disease-specific 13-item self-administered questionnaire for lung cancer was developed (EORTC QLQ-LC13; Appendix I) to be used in conjunction with the EORTC QLQ-C30 (Bergman et al 1994). It comprises both multi-item and single-item measures of lung cancer-associated symptoms (ie, coughing, hemoptysis, dyspnea, and pain) and side effects from conventional chemotherapy and radiotherapy (ie, hair loss, neuropathy, sore mouth, and dysphagia). Similar to the EORTC QLQ-C30, all questions except one have a 4-point scale: “not at all”, “a little”, “quite a bit” and “very much”. One question (no. 43, “Did you take any medicine for pain?”) has a response option of “yes” or “no”. The scoring approach for the EORTC QLQ-LC13 is similar to the EORTC QLQ-C30.

8.2.7.3 PRO-CTCAE

The PRO-CTCAE is included to address tolerability from the patients’ perspective. It was developed by the National Cancer Institute (NCI). The PRO-CTCAE will only be administered in those countries where a linguistically validated version exists. It was developed in recognition that collecting symptom data directly from patients using PRO tools can improve the accuracy and efficiency of symptomatic AE data collection. This was based on findings from multiple studies demonstrating that physicians and nurses underestimate symptom onset, frequency, and severity in comparison with patient ratings (Antonia et al 2014, Litwin et al 1998, Sprangers and Aaronson 1992). These symptoms have been converted to patient terms (eg, the CTCAE term “myalgia” has been converted to “aching muscles”). For several symptoms, like fatigue and pain, additional questions are asked about symptom frequency, severity, and interference with usual activities. The items included in the PRO-CTCAE have undergone extensive qualitative review among experts and patients. These items have been extensively evaluated by cancer patients to be clear, comprehensible, and measure the symptom of interest. In this study, only items that are considered relevant for the study, site of cancer, and cancer treatment are selected.

8.2.7.4 Administration of the patient-reported outcome questionnaires

Patients will complete the PRO assessments in paper format during clinic visits. Each center must allocate the responsibility for the administration of the PRO instruments to a specific individual (eg, a research nurse or study coordinator) and, if possible, assign a back-up person to cover if that individual is absent. The PRO questionnaires must be administered and completed at the clinic as per the schedule of assessments. The PRO questionnaires will be administered on the days specified in the schedules of assessments. The EORTC QLQ-C30 should always be completed prior to the EORTC QLQ-LC13 module.

It is important that the significance and relevance of the data are explained carefully to participating patients so that they are motivated to comply with data collection. The following best practice guidelines should be followed when collecting PRO data:

- It is preferred that PRO questionnaires are completed prior to any other study procedures (following informed consent) and before discussion of disease progression to avoid biasing the patient’s responses to the questions.

- PRO questionnaires must be completed in private by the patient.
- Patients should be given sufficient time to complete the PRO questionnaires at their own speed.
- The research nurse or appointed site staff should stress that the information is confidential. Therefore, if the patient has any medical problems, he/she should discuss them with the doctor or research nurse separately from the ePRO assessment.
- The research nurse or appointed site staff must train the patient on how to complete the questionnaires. The research nurse or appointed site staff must remind patients that there are no right or wrong answers and avoid introducing bias by not clarifying items. The patient should not receive help from relatives, friends, or clinic staff to answer the PRO questionnaires.

8.2.8 Health care resource use

The assessment of health care resource use will increase the understanding regarding the relationship between treatment and tumor-related cancer symptoms on resource use, such as the need for palliative procedures to address obstruction and bleeding. This will be captured and analyzed to inform submissions to payers. To investigate the impact of treatment and disease on health care resource use, the following variables will be captured:

- Number and length of hospitalizations.
- Number of visits to oncology service.
- Number of emergency visits.
- Number of outpatient visits.
- Number of imaging tests.
- Number of biopsy-related procedures.
- Treatment name, dose, duration, number of cycles.

8.2.9 Other safety assessments

If new or worsening pulmonary symptoms (eg, dyspnea) or radiological abnormality suggestive of pneumonitis/ILD is observed, toxicity management as described in detail in the Dosing Modification and Toxicity Management Guidelines (see Section 8.4.5) will be applied. The results of the full diagnostic workup (including high-resolution computed tomography [HRCT], blood and sputum culture, hematological parameters, etc) will be captured in the eCRF. It is strongly recommended to perform a full diagnostic workup, to exclude alternative causes such as lymphangitic carcinomatosis, infection, allergy, cardiogenic edema, or pulmonary hemorrhage. In the presence of confirmatory HRCT scans where other causes of respiratory symptoms have

been excluded, a diagnosis of pneumonitis (ILD) should be considered and the Dosing Modification and Toxicity Management Guidelines should be followed.

Pneumonitis (ILD) investigation

The following assessments, and additional assessments if required, will be performed to enhance the investigation and diagnosis of potential cases of pneumonitis. The results of the assessment will be collected.

- Physical examination
 - Signs and symptoms (cough, shortness of breath, and pyrexia, etc) including auscultation for lung field will be assessed.
- SpO₂
 - Saturation of peripheral oxygen (SpO₂)
- Other items
 - When pneumonitis (ILD) is suspected during study treatment, the following markers should be measured where possible:
 - (i) ILD Markers (KL-6, SP-D) and β -D-glucan
 - (ii) Tumor markers: Particular tumor markers which are related to disease progression.
 - (iii) Additional Clinical chemistry: CRP, LDH
 - (iv) Any test to rule out an active infectious disease and any other causes should be performed under investigator criteria.

8.3 Collection of adverse events

The Principal Investigator is responsible for ensuring that all staff involved in the study are familiar with the content of this section

The definitions of an AE or SAE can be found in Appendix B.

AE will be reported by the patient (or, when appropriate, by a caregiver, surrogate, or the patient's legally authorized representative).

The Investigator and any designees are responsible for detecting, documenting, and recording events that meet the definition of an AE or SAE. For information on how to follow/up AEs see Section 8.3.3.

8.3.1 Method of detecting AEs and SAEs

Care will be taken not to introduce bias when detecting AEs and/or SAEs. Open-ended and non-leading verbal questioning of the patient is the preferred method to inquire about AE occurrences.

8.3.2 Time period and frequency for collecting AE and SAE information

AEs and SAEs will be collected from the time of the patient signing the informed consent form until the follow-up period is completed (90 days after the last dose of durvalumab). If an event that starts post the defined safety follow up period noted above is considered to be due to a late onset toxicity to study drug then it should be reported as an AE or SAE as applicable.

All SAEs will be recorded and reported to the Sponsor or designee within 24 hours, as indicated in Appendix B. The Investigator will submit any updated SAE data to the Sponsor within 24 hours of it being available.

Investigators are not obligated to actively seek AE or SAE in former study patients. However, if the Investigator learns of any SAE, including a death, at any time after a patient's last visit and he/she considers the event to be reasonably related to the Study treatment or study participation, the Investigator should notify the Sponsor.

The method of recording, evaluating, and assessing causality of AE and SAE and the procedures for completing and transmitting SAE reports are provided in Appendix B.

8.3.3 Follow-up of AEs and SAEs

After the initial AE/SAE report, the Investigator is required to proactively follow each patient at subsequent visits/contacts. All SAE/non-serious AEs/AEs of special interest, will be followed until resolution, stabilization, the event is otherwise explained, or the patient is lost to follow-up

Any AEs that are unresolved at the patient's last AE assessment in the study are followed up by the Investigator for as long as medically indicated (this may be beyond the 90 days after the last dose of durvalumab), but without further recording in the CRF. AstraZeneca retains the right to request additional information for any patient with ongoing AE(s)/SAE(s) at the end of the study, if judged necessary.

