2.3.2.2 Durvalumab + chemotherapy

The safety and tolerability of the combination of durvalumab plus chemotherapy was evaluated in two early studies evaluating different chemotherapy regimens in patients with solid tumors: AZ study D419SC00001 and CCTG study NCT02537418. In general, the combination of durvalumab plus tremelimumab with chemotherapy appeared tolerable and manageable. On all dose levels, dose delays of durvalumab were mostly for administrative reasons/patient request and neutropenia related to chemotherapy.

In the randomized phase III CASPIAN study, durvalumab + EP was well tolerated with a manageable safety profile as first line treatment for ES-SCLC. The safety profile was consistent with the known profile of all the agents and no new safety signals were identified (Paz-Ares 2019). In summary, regardless of causality, rates of AE of any grade (98.1% vs 97.0%), grade 3 or 4 AE (61.5% vs 62.4%), serious AEs (30.9% vs 36.1%), and those leading to discontinuation (9.4% vs 9.4%) were similar between durvalumab + EP vs EP alone. Adverse events of any cause leading to death occurred in 13 (5%) and 15 (6%) patients. The most common adverse events were haematological toxicities. Immune-mediated adverse events, defined as an event that is associated with drug exposure and consistent with an immune-mediated mechanism of action, where there is no clear alternate aetiology and the event required treatment with systemic corticosteroids or other immunosuppressants and/or, for specific endocrine events, endocrine therapy, were reported by 19.6% of patients treated with durvalumab + EP compared to 2.6% of patients treated with EP alone. The majority of immune-mediated AEs were low grade and thyroid related, consistent with the known safety profile of durvalumab.

External clinical data also supports these findings. In the randomized Phase III study IMpower133 demonstrated that the safety profile of atezolizumab combined with etoposide plus carboplatin was consistent with the previously reported safety profile of the individual agents, with no new findings observed (Horn 2018).

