8.3.4 Adverse event data collection

The following variables will be collected for each AE:

- AE (verbatim)
- The date when the AE started and stopped
- The maximum CTCAE grade reported
- Changes in CTCAE grade (report only the maximum CTCAE grade for a calendar day)

- Whether the AE is serious or not
- Investigator causality rating against the IPs (yes or no)
- Action taken with regard to IPs
- Administration of treatment for the AE
- Outcome

In addition, the following variables will be collected for SAEs:

- Date the AE met criteria for SAE
- Date the Investigator became aware of the SAE
- Seriousness criteria
- Date of hospitalization
- Date of discharge
- Probable cause of death
- Date of death
- Whether an autopsy was performed
- Causality assessment in relation to study procedure(s)
- Causality assessment in relation to other medication, as explained in Section 8.3.5
- Description of the SAE

The grading scales found in the revised NCI CTCAE version 5.0 will be utilized for all events with an assigned CTCAE grading. For those events without assigned CTCAE grades, the recommendation in the CTCAE criteria that converts mild, moderate, and severe events into CTCAE grades should be used. A copy of the CTCAE version 5.0 can be downloaded from the Cancer Therapy Evaluation Program website (<http://ctep.cancer.gov>).

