#### Endpoints analyzed:

- Incidence of grade  $\geq 3$  AEs
- Incidence of imAE.

This analysis will be performed for Safety analysis set. For all summaries of AEs, only treatment-emergent AEs will be included. Treatment-emergent AEs are defined as events present at baseline that worsen in intensity after administration of IP or events absent at baseline that emerge after administration of IP, for the period extending to 90 days after the last dose of IP.

The analysis will be performed with the information completed into the adverse event eCRF section.

Total SAEs, AESIs, AEs leading to death, and AEs leading to study drug interruption or discontinuation will be summarized by Medical Dictionary for Regulatory Activities (MedDRA) by System Organ Class (SOC) and Preferred Term (PT), causality, and maximum NCI CTCAE Grade. Deaths from all causes will be also summarized.

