## **5. ANALYSIS METHODS**

Descriptive statistics will be used for all variables, as appropriate. Continuous variables will be summarized by the number of observations, mean, standard deviation, median, quartiles (Q1 and Q3), minimum, and maximum. Categorical variables will be summarized by frequency counts and percentages for each category. The number of missing data will be provided for every analysed variable.

Missing values will not be considered for calculating percentages or any other descriptive, meaning that only valid values will be presented. No use of any method for the handling of missing data is foreseen.

For patients excluded from the statistical analyses, descriptive of the reasons for non-evaluability will be provided.

The software package SAS version 9.4 will be used for data analysis.

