### Endpoints analyzed:

- Incidence of grade  $\geq 3$  AEs
- Incidence of imAE.

Safety data will be summarized descriptively overall, by seriousness, by causality, and by maximum NCI CTCAE Grade. The exact 95% CIs around the incidence of Grade 3 and Grade 4 AEs will be reported. All outputs will be summarized for the Safety analysis set.

A subgroup analysis may be conducted in the following subgroups, assuming sufficient sample size per subgroup: platinum therapy receiving (carboplatin or cisplatin), age, gender, performance status, smoking status and CNS metastasis at baseline (Yes/No).

For this aims, the following summaries of AEs will be provided:

- Number and percentage of patients with AEs in total and by causality and severity
- Number and proportion of patients with Grade 3 and Grade 4 AEs in total and by causality
- Number and proportion of patients with SAEs in total and by causality
- Number and proportion of patients with AEs leading to death
- Number and proportion of patients with AEs leading to treatment interruption and/or discontinuation
- Number and proportion of patients with AESI, by predefined type (or newly defined by this study) in total and by seriousness, severity and causality, including immune relatedness
- Number and proportion of patients who received steroids, immunosuppressants, and/or hormone replacement therapy to manage AESIs
- Time from start of durvalumab to the onset of an AESI predefined type, all interventions of AESIs by type of intervention (including intervention with steroids, immunosuppressants, and/or hormone replacement therapy), and time from onset of an AESI type to resolution.
- Duration of the intervention with steroids, immunosuppressants, and/or hormone replacement therapy until the resolution of AESI.
- Number and proportion of patients with imAEs. The imAEs will be assessed as a subset of AESIs. An imAE is defined as an AESI that is associated with drug exposure and is consistent with an immune-mediated MOA and where there is no clear alternate etiology.
- Listing of SAEs per patient, including the following variables:
  - Patient ID
  - AE number
  - AE description
  - PT Term
  - Grade NCI-CTCAE v5.0 (1-5)
  - Onset date (DD-MMM-YYYY)

- End date (DD-MMM-YYYY)
- Ongoing (Yes; No)
- Outcome
- Seriousness criteria
- AESI (Yes; No)
- Relationship
- Action taken

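### The SAP's two AESI duration summaries have no censoring rule, so events still ongoing at the last AE assessment drop out and the reported durations are biased short

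*Protocol*

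**What the plan says.** Protocol 8.3.2 collects adverse events from consent "until the follow-up period is completed (90 days after the last dose of durvalumab". For each event, Protocol 8.3.4 records "The date when the AE started and stopped", together with its outcome. Under Protocol 8.3.3 an event unresolved at the last AE assessment is still followed clinically ("this may be beyond the 90 days after the last dose of durvalumab), but without further recording in the CRF").

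SAP 4.2.1 names the data source: "The analysis will be performed with the information completed into the adverse event eCRF section". From it, SAP 5.1 commits to two duration outputs. One is the time from onset of an AESI to its resolution. The other is "Duration of the intervention with steroids, immunosuppressants, and/or hormone replacement therapy until the resolution of AESI".

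SAP 5 sets the general rule: "Missing values will not be considered for calculating percentages or any other descriptive, meaning that only valid values will be presented". SAP 6.2 repeats it and foresees no imputation or other handling. The number of missing values is to be given for each variable. SAP 4.2.2 defines censoring for PFS, OS, duration of response and PRO deterioration. It defines none for the two AESI durations.

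**The concern.** Both outputs end at resolution. An event that is ongoing when recording stops has an onset date and no end date, so neither duration can be calculated for it as a complete value. Under the general rule it is a missing value and leaves the summary. Whether an event is missing therefore depends on the quantity being measured, because the longest events are the ones removed.

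At stake is the description of how long immune toxicity and its treatment last, within a study whose primary objective is to describe safety. Of the earlier phase III trial of this regimen, the protocol says: "The majority of immune-mediated AEs were low grade and thyroid related". Its AESI description (Protocol 8.3.13) includes events that may need hormone replacement. If some of these continue on treatment past the last AE assessment, the two summaries would describe only the events that ended.

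**Working it through.** **The plan's own figure.** Protocol 9.2 gives an exact 95% interval of 12.1 to 30.1% (±9.0 points) for a 20% imAE incidence in 85 patients. With 0.20 × 85 = 17 events, Clopper-Pearson gives 12.10 to 30.08%, half-width 8.99 points, which agrees. This is an incidence figure and the present point does not change it. It is used here only for scale: about 17 patients with an imAE. AESIs are a broader set, so the number with an AESI may be larger. The documents state no figure for AESI duration or resolution.

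**Direction.** Let T be the time from onset to resolution and W the time from onset to the last AE assessment. A resolved-only summary describes T given T ≤ W. If W does not depend on T, a duration t enters with weight P(W ≥ t), which falls as t grows. The summarised distribution is therefore shifted towards short durations, whatever the distribution of T.

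**Size, fixed window (assumed inputs).** Take T exponential with true median M, and suppose all events eventually resolve.

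- Proportion dropped = 2^(−W/M)
- Resolved-only median = −M × log2(1 − F/2), with F = 1 − 2^(−W/M)

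Worked example, M = 90 and W = 90: F = 1 − 0.5 = 0.5, so the resolved-only median is −90 × log2(0.75) = 37.4 days, with 50% dropped.

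W = 90 corresponds to onset at about the last dose. Earlier onset gives a longer window.

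| True median (days) | Window (days) | Dropped | Of 17 | Resolved-only median (days) | Ratio to true |
|---|---|---|---|---|---|
| 30 | 180 | 1.6% | 0.3 | 29.3 | 0.98 |
| 60 | 180 | 12.5% | 2.1 | 49.8 | 0.83 |
| 60 | 90 | 35.4% | 6.0 | 33.8 | 0.56 |
| 90 | 180 | 25.0% | 4.2 | 61.0 | 0.68 |
| 90 | 90 | 50.0% | 8.5 | 37.4 | 0.42 |
| 180 | 180 | 50.0% | 8.5 | 74.7 | 0.42 |
| 180 | 90 | 70.7% | 12.0 | 41.1 | 0.23 |

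**Size, varying window, and what censoring recovers.** This simulation used 400,000 events, W uniform between 90 and 270 days, and medians of 30, 60 and 90 days among events that do resolve. A share never resolves. Deaths were not simulated.

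| Share never resolving | Resolved-only median (days) | Kaplan-Meier median (days) |
|---|---|---|
| 0% | 28.7 / 48.0 / 59.1 | 29.9 / 60.1 / 90.1 |
| 25% | 28.7 / 48.1 / 59.0 | 47.6 / 94.7 / 142.7 |
| 50% | 28.7 / 47.9 / 58.9 | not reached in all three |

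The resolved-only median hardly moves as the share of persistent events rises. The censored estimate does respond, and with no persistent events it recovers the true medians.

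**The case against.** The strongest reply is that little is lost. Unresolved AESIs stay in the tables by type, seriousness, severity and causality, in the imAE incidence, and in the count of patients treated for AESIs. Outcome is collected for every event, missing counts are reported, and the SAE listing carries an ongoing flag. Protocol 8.3.3 adds: "AstraZeneca retains the right to request additional information for any patient with ongoing AE(s)/SAE(s) at the end of the study". Protocol 9.4 offers the duration measures only as ones that may be included. Finally, no sentence says that ongoing AESIs are excluded; that follows from a general missing-data rule.

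Most of this stands, and it limits the point. A reader might infer that long-lasting immune events disappear from the trial, or that the primary endpoints are biased. The documents do not support either, because incidence does not require resolution. Nor do they support reading the CRF cut-off as a fault: ending recording at the last AE assessment is ordinary administrative censoring. It would also go too far to say that the trial cannot tell who has a persistent event, since the outcome field holds that information. The imAE definition with a treatment criterion, including endocrine therapy, belongs to the earlier phase III trial (Protocol 2.3.2.2), not to this study. That thyroid events are the ones most likely to be open at 90 days is stated nowhere.

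The missing rule remains. Whatever Protocol 9.4 leaves optional, SAP 5.1 commits to both outputs. The sponsor's right to ask for more data is discretionary. A missing count does not separate an ongoing event from an unrecorded date, and SAP 5.1 specifies the ongoing flag only for serious events. The SAP also treats its nearest analogue in the same way: time to treatment discontinuation is summarised only in patients who discontinued (SAP 4.2.2.1).

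**Conclusion.** The point holds as a gap in the SAP confined to two descriptive outputs. Followed as written, the plan summarises the duration of resolved AESIs only, and both durations are biased short. That ongoing events are dropped is inferred from the general rule, but the SAP gives no other instruction.

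The documents do not give the size. Under exponential resolution, the resolved-only median is 2% short for a 30-day true median seen over 180 days, and 58% short for a 90-day true median seen over 90 days. The 90-day window is near the unfavourable end and should not be read as typical, since collection also covers the whole treatment period. Persistent events increase the bias, but their share is an assumption here.

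**What to change.** Amend SAP 5.1 and 6.2 as follows.

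- Exempt time to AESI resolution and duration of intervention from the valid-values-only rule.
- Analyse both as time-to-event outcomes, with unresolved AESIs censored at the last AE assessment. Use cumulative incidence with death before resolution as a competing event. If Kaplan-Meier is preferred, state the limitation that death is then treated as ordinary censoring.
- Report the number and percentage of AESIs unresolved at the last AE assessment, by AESI type.
- Apply the same rule to the output of SAP 5.1 that SAP 7 schedules for October 2021, censoring at the last AE assessment before that cut.

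No change to CRF recording under Protocol 8.3.3 is needed. Onset date, stop date and outcome are already collected, so the cost is SAP wording and a little more analysis work.
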